3.2 Secondary Objectives

- A) To assess feasibility and acceptability of recruiting STI prophylaxis users via sexual health clinics versus online and obtaining appropriate samples.
- B) To evaluate the use of shotgun metagenomic sequencing to identify AMR genes or gene mutations conferring resistance to tetracycline and other relevant antibiotic classes.
- C) To evaluate the use of shotgun metagenomic sequencing to identify bacteria present in the gastrointestinal tract and oropharynx of MSM.
- D) To estimate the prevalence of AMR genes/gene mutations of interest and describe changes over time in the gastrointestinal tract and oropharynx of MSM using and not using STI prophylaxis.
- E) To characterise the gastrointestinal and oropharyngeal microbiomes and describe changes over time in MSM using and not using STI prophylaxis.
- F) To develop the methodology for future AMR research and surveillance in MSM and other relevant population groups.

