4.2 Study Timeline

Aim for REC Approval	Jan 2025
Study site R&D approval and site setup	Jan 2025
Recruitment (Visit 1) window	Jan 2025 – Jul 2025
Sample processing starts	Oct 2024
Follow-up visit 2 window	Apr 2025 – Jan 2026
Visit 1 samples bacterial genomic sequencing & analysis	Jul 2025 – Sep 2025
Follow-up Visit 3 window	Oct 2025 – Jul 2026
Last participant last study visit	Jul 2026
Sample processing end	Jul 2026
Visits 2 & 3 sample sequencing & complete analysis	Jul 2026 – Apr 2027

See *Section 5 Study Schedule* for more information on study visits.

End of study: The end of the study is defined as once all study visits for every participant have been completed, all study samples processed and undergone bacterial genomic sequencing, and data has been checked and locked. Data analysis will be ongoing at the end of the study.

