- **At home after study visit:** participants will be able to provide a stool sample collected at home within 7 days of the study visit and return the sample to the study site within 48 hours of collection.

- **At home before study visit:**
 - **Visit 1:** participants completing e-consent and opting to be posted a stool sample collection kit will collect the sample at home less than 48 hours before the study visit and to bring it with them.
 - **Visits 2 and 3:** At Visit 1, participants will be given kits for follow-up visits to take home and return when they attend for Visits 2 and 3. Participants will be asked to collect the sample at home less than 48 hours before the visit.

Stool samples will be labelled with the date of collection, the participant ID, and a sample ID number.

Sample Storage and Transport

[figure not shown]
Samples will be labelled with the date of collection, unique participant ID, and a sample ID number. Samples will be stored at the study site at -80C for a maximum of 28 days, before being couriered in an appropriate container for microbiology samples to the University of Oxford laboratory (Department of Biology, University of Oxford, [name]) for processing and storage until the end of the study (see **Figure 1** and *Section 13 Material/Sample Storage and Storage*). No study samples will be stored beyond the end of the expected study completion of April 2027.

Sample Processing and Sequencing

Sample specific microbial DNA extraction kits will be used. Extracted bacterial DNA will be stored at the Department of Biology, University of Oxford at -80C prior to metagenomic sequencing. Library preparation and metagenomic sequencing will be undertaken at UCL Genomics ([name]).

Participants will remain in the study for a maximum of 13 months (360 +/- 30 days) (see *Section 5 Study Schedule*)

Figure 1: Sample workflow for Visits 1, 2, and 3.

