9 DATA ANALYSIS

9.1 Statistical Analysis

The planned statistical analysis is summarised here. The statistical analysis will be fully outlined in a statistical analysis plan (SAP). The SAP will be written by [name] (Chief Investigator) and [name] (Co-Investigator & Statistician). The SAP will be finalised before any analysis takes place. An analysis of baseline samples will be undertaken once all participants have completed Visit 1.

Sample characteristics, STI prophylaxis use, and questionnaire responses will be described using absolute numbers and proportions. A pooled prevalence estimate with 95% CI for AMR genes/gene mutations of interest will be produced. Chi-square tests will be used to evaluate evidence of differences in prevalence between subgroups, although findings will be presented with caution given the relatively small sample size. The association between detection of AMR genes/gene mutations of interest with demographic and sexual history variables will be described and investigated in exploratory univariable analyses.

Descriptive analyses of AMR detection over time within each group will be conducted. If adequate variation within individuals over time, then generalised estimating equations logistic regression will explore trends over time and consistency of AMR detection within each group.

Statistical analyses will be undertaken on the statistical programmes STATA and R.

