9.2 Bioinformatic Analysis

The bioinformatic methodology and analysis is summarised here. The bioinformatic analysis will be fully outlined in a bioinformatic analysis plan (BAP). The BAP will be written by [name] (Chief Investigator) and [name] (Co-Investigator & Bioinformatician).

Bacterial taxonomic profiling will use both de novo assembly and read-mapping approaches. De novo assembly tools (e.g., MEGAHIT, metaSPAdes) will allow evaluation of taxonomy and AMR genetic diversity. Supervised binning methods will group assembled contigs (DNA sequences) by species using tools such as metaBAT, and the PubMLST/metaMLST reference databases which hosts assembled whole genome sequence data from over 480,000 bacterial isolates. Antibiotic resistance databases (e.g., Comprehensive Antibiotic Resistance Database) will be used to identify genes conferring resistance to tetracyclines (e.g., *tet(M)*, *tet(W)*, *tet(Q)*) and other important antibiotic classes (e.g., Macrolides *mphA*, *ermF*).

To mitigate potential assembly problems from low-abundance organisms, read mapping approaches will be undertaken using the pipeline CCMetagen which uses the National Centre for Biotechnology Information (NCBI) database as reference. Computationally intensive analyses will be carried out in a single *in silico* system that archives and integrates bacterial metagenomes and AMR genes with other rich metadata, and can organise and share genomes to allow integrated analyses and modelling.

Genome-wide association study analyses incorporating machine learning will identify core and accessory genome AMR elements (including plasmids) from complex samples. Genomic variation identified will include gene presence and absence; gene orthologs/alleles; insertions/deletions and single nucleotide polymorphisms (SNPs). These will be linked to AMR and other metadata.

Bacterial genera diversity (microbiome profiles) and AMR genes/gene mutations of interest ('resistome' profiles) will be compared between baseline study groups, and over time by use of doxycycline prophylaxis. Exploratory analysis of microbiome profiles by other characteristics including HIV status and sexual history will be undertaken.

This study does not analyse human DNA.

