13 MATERIAL/SAMPLE TRANSPORT AND STORAGE

Stool samples and oropharyngeal swabs will be collected from patients in accordance with the patient consent form and patient information sheet and shall include all tissue samples or other biological materials and any derivatives, portions, progeny or improvements as well as all patient information and documentation supplied in relation to them. Samples will be processed, stored and disposed in accordance with all applicable legal and regulatory requirements, including the Human Tissue Act 2004 and any amendments thereafter, and the applicable HTA Codes of Practice Departmental SOPs will be followed to facilitate regulatory compliance.

Samples will be labelled with the unique participant ID, a sample ID number, and date of collection. Study site sample collection, storage and storage SOPs will be written by [name] (CI/PI). Samples will be stored at the study site in a freezer (lowest temperature -80C) for a maximum of 28 days, before being couriered in an appropriate container for microbiology samples to the University of Oxford laboratory (Department of Biology, University of Oxford, [name]) for processing and storage at -80C until the end of the study. Samples will be processed as quickly as possible after collection and courier. An MTA will be in place prior to any sample collection and transfer. A study specific laboratory SOP, adapted from existing local SOPs and DNA extraction kit protocols, will be written by [name] (Chief Investigator) and [name] (Co-Investigator and Microbiologist) prior to any sample processing. No study samples will be stored beyond the end of the expected study completion of April 2027 and will be destroyed in line with local health and safety protocols.

Samples will be processed at the University of Oxford, Department of Biology laboratory. Samples will undergo bacterial DNA extraction. Extracted bacterial DNA will be stored at the University of Oxford Department of Biology at -80C prior to metagenomic sequencing. Metagenomic sequencing will be undertaken at UCL Genomics ([name]).

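### Section 9.1 follows AMR detection only within enrolment groups, so change from Visit 1 cannot be told apart from a shift between the two sequencing windows (minor)

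*Protocol*

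**What the plan says.** **Timing of sequencing.** The timeline in section 4.2 has one row for "Visit 1 samples bacterial genomic sequencing & analysis", dated July to September 2025, and one for "Visits 2 & 3 sample sequencing & complete analysis", dated July 2026 to April 2027. The split serves an early look at the data. Section 9.1 states: "An analysis of baseline samples will be undertaken once all participants have completed Visit 1".

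**Analysis over time.** Section 9.1 plans descriptive analyses of AMR detection over time inside each group. If individuals vary enough, "generalised estimating equations logistic regression will explore trends over time and consistency of AMR detection within each group". Its only stated test between subgroups is a chi-square test on prevalence; it names no contrast of change between groups. Section 4.1 fixes the groups at enrolment from antibiotic exposure in the preceding 3 months.

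**Related statements.** Secondary objective D in section 3.2 is to estimate prevalence and "describe changes over time in the gastrointestinal tract and oropharynx of MSM using and not using STI prophylaxis". Section 4.4 collects prophylaxis use by questionnaire at every visit. Section 9.2 says that microbiome and resistome profiles "will be compared between baseline study groups, and over time by use of doxycycline prophylaxis".

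**The concern.** Every participant's baseline sample falls in one sequencing window and every follow-up sample in the other. A model fitted inside one group has no samples from different visits within the same window that would link Visit 1 to follow-up. If the detection rate differs between windows for technical reasons, an upward difference looks like AMR emergence and a downward one can hide a real rise.

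A related, smaller mismatch is that 9.1 uses the enrolment label while objective D and section 9.2 speak of use. Visit 2 falls on days 150 to 210. Taking 3 months as 90 days, a look-back from Visit 2 starts no earlier than day 150 − 90 = 60. The enrolment label therefore need not describe exposure at follow-up.

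At stake is how a secondary, exploratory result is read. Objective F is to develop methods for later surveillance, so the limitation should be stated where the analysis is defined.

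**Working it through.** **1. The plan's own figures (section 4.3).** With prevalence 0.325, the half-width is 1.96 × √(0.325 × 0.675 / n). This gives 8.83% at n = 108 (stated 8.85%) and 15.3% at n = 36 (stated 15.5%; 15.5% with n − 1). P(at least 6 of 36) = 0.990 (stated 99%). These figures are sound and the point does not depend on them.

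**2. Aliasing.** For one group, code an intercept, Visit 2, Visit 3 and second window:

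| Visit | Intercept | V2 | V3 | Window 2 |
|---|---|---|---|---|
| 1 | 1 | 0 | 0 | 0 |
| 2 | 1 | 1 | 0 | 1 |
| 3 | 1 | 0 | 1 | 1 |

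Window 2 = V2 + V3, so the rank is 3 with 4 columns. More participants do not change this. In a three-group model with group-by-visit terms (9 columns, rank 9), adding the window column leaves the rank at 9. The window is absorbed by the visit main effects, and the interaction terms stay interpretable if the shift is common to all groups.

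**3. A simple example (assumed detection rates).** Let true prevalence stay at 32.5%, with 80% of carriers detected in window 1 and 100% in window 2. The false within-group rise is 0.325 × (1.00 − 0.80) = 6.5 points. The difference in change between groups is 0 if their prevalences are equal. With prevalences of 45% and 30% it is 0.45 × 0.20 − 0.30 × 0.20 = 3 points, so a contrast removes most of the shift, not all of it.

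**4. Simulation (all effects assumed).** Random-intercept logistic data with SD 1.5; 32.5% marginal detection at baseline; 36 per group; 3 visits; 10% loss per visit; 70% of Group A and 30% of Groups B and C using prophylaxis at each follow-up visit; exchangeable GEE with robust standard errors; two-sided 5% level; 4,000 runs. Shifts are participant-level odds ratios (OR). OR 2 moves marginal detection from 32.5% to 44.1%, a marginal OR of (0.441/0.559)/(0.325/0.675) = 1.64.

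Rejection rates with a shift common to all groups and no true change:

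| Shift OR | 1/3 | 1/2 | 1 | 1.5 | 2 | 3 |
|---|---|---|---|---|---|---|
| Marginal detection at follow-up | 18% | 23% | 32.5% | 39% | 44% | 51% |
| Within-group trend | 36% | 19% | 6% | 11% | 22% | 46% |
| Group-by-visit (4 df) | 5% | 6% | 6% | 6% | 6% | 6% |
| Visit-level use term | 6% | 6% | 6% | 6% | 5% | 6% |

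- A real rise of OR 2 in every group with no shift gives 22% for the trend, the same as a shift of OR 2 with no real rise.
- Masking: with a real rise of OR 3 in Group A only, an upward trend in A is found in 46% of runs with no shift, 11% with a shift of OR 1/2 and 3% with OR 1/3.

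**5. What the alternative contrasts cost.**
- With a shift of OR 2 and a same-visit use effect of OR 2 or 3, group-by-visit has power 8% or 13%.
- The use term has 54% or 89%, from a model with visit and use terms only; adding enrolment-group terms lowers this.
- If use acts only through the previous visit, the same-visit use term stays at about 6%.
- If the shift is unequal (OR 3 in A, 1.5 in B and C), group-by-visit rejects in 12% and the use term in 6%.
- Under a real rise of OR 2 common to all groups, the use term and group-by-visit stay at 5% and 6%: the visit terms absorb that rise.

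**The case against.** **Deferral to other documents.** Section 9.1 is a summary, with detail left to a SAP, a bioinformatic plan and a laboratory SOP that are not shown. Any of these may add a contrast, batch records or re-sequencing, and their absence here is no finding. That stands. The point rests only on an analysis that 9.1 states and a schedule that 4.2 fixes.

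**Group C.** The trend is reported in all three groups, so a common shift would also appear in Group C. That stands as an informal check, not as an estimated contrast.

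**One laboratory chain.** Sequencing is planned at one facility, and the computationally intensive analyses run in one in silico system. Both may reduce a shift; neither excludes it.

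**Stronger readings that the documents do not support.**
- A reader might infer that a shift will occur or that the results will be wrong. No shift size is given, and every rejection rate above is conditional on an assumed one. At an assumed OR of 1.25 the trend rejects in about 6% of groups, close to nominal.
- A reader might infer that no comparison over time by use is planned. Section 9.2 plans one.
- A reader might take the second window as ten months of sequencing and conclude that Visit 3 versus Visit 2 is confounded in the same way. That row also covers the complete analysis and puts both visits together. Samples are extracted on a rolling basis ("Samples will be processed as quickly as possible after collection and courier") and the visit windows overlap, so extraction date is not tied to visit as sequencing window is.
- A reader might infer that the primary objective is undermined. It concerns feasibility and acceptability, and objective D is descriptive.

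**Conclusion.** The point holds as a minor one. Under sections 4.2 and 9.1 as written, a within-group change from Visit 1 is exactly confounded with sequencing window and is not by itself evidence of AMR emergence. The aliasing follows from the design and needs no assumption. Its practical size is unknown: under the assumed model, the false-positive rate of the within-group trend goes from about 6% with no shift to about 22% at a participant-level OR of 2. Section 9.2 already contains a comparison by use, so the gap lies in 9.1 and in its alignment with 9.2. No primary result or sample-size figure depends on this analysis, which is exploratory and runs only if within-person variation is adequate.

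**What to change.** In section 9.1:

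- **(a)** Keep the within-group descriptions and trends. State that change from Visit 1 is confounded with sequencing window and is not by itself evidence of AMR emergence.
- **(b)** If within-person variation is adequate, add a pooled GEE over all participants with categorical visit terms and visit-level doxycycline prophylaxis use, defined as in 9.2. Report the enrolment group-by-visit contrast as a secondary description.
- **(c)** Record sequencing run and extraction date for each sample.

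State the limits alongside. These contrasts remove only a shift common to all groups on the logit scale. Visit terms also absorb a real rise common to all groups. Group-by-visit power is low (about 8% to 13% in the illustration). The use term is an association open to confounding, for example by sexual behaviour.

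The cost is wording, two extra recorded fields and one further model. Use is already collected at each visit; the questionnaire's look-back period is not stated and should match the definition in 9.2.

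Re-sequencing some stored Visit 1 extracts with the follow-up samples is an optional laboratory check, not part of the required change. For example, 36 stool extracts would be 36 of up to 108 × 3 × 2 = 648 libraries (5.6%). It would test sequencing but not extraction. It would have to be arranged before storage ends: "No study samples will be stored beyond the end of the expected study completion of April 2027".

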9.2 Bioinformatic Analysis

The bioinformatic methodology and analysis is summarised here. The bioinformatic analysis will be fully outlined in a bioinformatic analysis plan (BAP). The BAP will be written by [name] (Chief Investigator) and [name] (Co-Investigator & Bioinformatician).

Bacterial taxonomic profiling will use both de novo assembly and read-mapping approaches. De novo assembly tools (e.g., MEGAHIT, metaSPAdes) will allow evaluation of taxonomy and AMR genetic diversity. Supervised binning methods will group assembled contigs (DNA sequences) by species using tools such as metaBAT, and the PubMLST/metaMLST reference databases which hosts assembled whole genome sequence data from over 480,000 bacterial isolates. Antibiotic resistance databases (e.g., Comprehensive Antibiotic Resistance Database) will be used to identify genes conferring resistance to tetracyclines (e.g., *tet(M)*, *tet(W)*, *tet(Q)*) and other important antibiotic classes (e.g., Macrolides *mphA*, *ermF*).

To mitigate potential assembly problems from low-abundance organisms, read mapping approaches will be undertaken using the pipeline CCMetagen which uses the National Centre for Biotechnology Information (NCBI) database as reference. Computationally intensive analyses will be carried out in a single *in silico* system that archives and integrates bacterial metagenomes and AMR genes with other rich metadata, and can organise and share genomes to allow integrated analyses and modelling.

Genome-wide association study analyses incorporating machine learning will identify core and accessory genome AMR elements (including plasmids) from complex samples. Genomic variation identified will include gene presence and absence; gene orthologs/alleles; insertions/deletions and single nucleotide polymorphisms (SNPs). These will be linked to AMR and other metadata.

Bacterial genera diversity (microbiome profiles) and AMR genes/gene mutations of interest ('resistome' profiles) will be compared between baseline study groups, and over time by use of doxycycline prophylaxis. Exploratory analysis of microbiome profiles by other characteristics including HIV status and sexual history will be undertaken.

This study does not analyse human DNA.

10 PATIENT AND PUBLIC INVOLVEMENT (PPI)

10.1 PPI for Funding Proposals and Study Design

Input was sought from:

- The Love Tank, who undertake advocacy work on LGBTQ+ health issues and provide information on STI/HIV prevention through their PrEPster and queerhealth.info programmes.
- The Terrence Higgins Trust and BASHH lay research panel.
- NIHR Research Design Service lay reviewers.
- Gay and bisexual men, through two workshops with six community members, funded by an NIHR PPI grant.

Overall, feedback was extremely supportive of the research and participants were clear that this was an important topic.

Changes made to the study on the advice of the PPI groups included:

- Revision of the research objectives to include changes in microbiome over time.
- Mechanisms to ensure ongoing PPI involvement in the study.
- Recruitment: dual strategy from sexual health clinics (to increase likelihood of participating) and online (to ensure inclusion opportunities for participants not attending clinics and from a wider geographical area).
- Study documents, promotional materials, and dissemination: to include clear understandable information about AMR, to use sensitive language to avoid contributing to stigma, and for information on STI prophylaxis should be balanced discussing both benefits and risks
- Co-production and collaboration: inclusion of co-production group and collaboration with trusted community organisations (see below).
- Stool samples: Collection of stool samples in clinic was acceptable, with provision options for participants to collect samples at home if they unable to provide a sample in clinic.

10.2 Community Advisory Group

The study includes a community advisory group. The group will meet regularly throughout study (online and/or in-person); and includes patients and community members. To date, the group have given input on the PIS and questionnaire; co-designed the online adverts/poster; and co-developed the recruitment strategies (see *Section 7 Recruitment*). Throughout the study, the group will monitor enrolment and advise on recruitment strategies as needed; co-analyse questionnaire data; co-develop dissemination plans; review the overall study findings; and co-produce community-focused outputs.

10.3 Collaboration with The Love Tank

The Love Tank is an LGBTQ+ and sexual health focused community organisation which runs the community programmes PrEPster and queerhealth.info. The Love Tank will be involved with online study promotion for community-based recruitment and community dissemination of the study findings.

11 FUNDING AND SUPPLY OF EQUIPMENT

The study funding has been reviewed by the UCLH/UCL Joint Research Office and deemed sufficient to cover the requirements of the study.

The research costs for the study have been supported by the National Institute for Health and Care Research (NIHR) Doctoral Fellowship £589,590 (NIHR303717), the British Infection Association (BIA) £10,000 (2023/[name]), and the British HIV Association (BHIVA) £9,979.96 (BHIVA/5020/2023/[name]).

